16.3 Safety

16.3.1 Tables

Number	Title	Analysis Set
14.3.1.1.1	Summary of AEs NCI CTCAE \geq 2 and Laboratory Features NCI CTCAE \geq 3 During the First 100 Days after Gene Therapy by SOC and Preferred Term	MS
14.3.1.2.1	Summary of Number of Subjects with an SAE within 48 Hours from Infusion by SOC and PT	MS
14.3.1.3.1	Summary of Subjects with Positive Replication Competent Lentivirus (RCL) Results	MS
14.3.2.1.1	Summary of Subjects with Positive Immune Response to Transgene	MS
14.3.2.2.1	Summary of Number of Subjects with Adverse Events by Treatment Phase	MS
14.3.2.2.2	Summary of All Adverse Events by SOC, Preferred Term and Treatment Phase	MS
14.3.2.2.3	Summary of Related Adverse Events by SOC, Preferred Term and Treatment Phase	MS
14.3.2.2.4	Summary of Serious Adverse Events by SOC, Preferred Term and Treatment Phase	MS
14.3.2.2.5	Summary of Unexpected Adverse Reactions by SOC, Preferred Term and Treatment Phase	MS [1]

Commentato [MS1]: Removed as it is not in TOC

14.3.2.2.6	Summary of Suspected Unexpected Serious Adverse Reactions by SOC, Preferred Term and Treatment Phase	MS [1]
14.3.2.2.7	Summary of All Adverse Events by Severity (Grade), SOC, Preferred Term and Treatment Phase	MS
14.3.2.2.8	Summary of Grade 3, 4, and 5 Adverse Events - 12 Months Pre- vs. Post-Gene Therapy	ITT [2]
14.3.2.2.9	Number and Rate of Most Frequently Reported Adverse Events (Rate \geq 1 per PYO in Any Treatment Phase) by Preferred Term	MS
14.3.2.2.10	Number (%) of Subjects with Autoimmunity Adverse Events of Special Interest by Preferred Term and Treatment Phase	MS
14.3.2.2.11	Summary of Adverse Events by Preferred Term, Ordered by Decreasing Frequency	MS
14.3.2.2.12	Number (%) of Subjects with Immune Mediated Adverse Events by Preferred Term and Treatment Phase	MS
14.3.2.2.13	Number (%) of Subjects with Eczema and Dermatological Adverse Events by Preferred Term and Treatment Phase	MS
14.3.2.2.14	Number (%) of Subjects with Autoimmunity Adverse Events based on Dictionary Defined Terms by Preferred Term and Treatment Phase	MS
14.3.2.3.1	Summary Statistics for Laboratory Parameters	MS
14.3.2.3.6	Summary of Shifts from Baseline to Maximum and Minimum Values for Lab Parameters	MS
14.3.2.3.7	Summary of Laboratory Data Relative to Normal Range Over Time	MS
14.3.2.3.8	Summary Statistics for Immunoglobulins	MS
14.3.2.4.1	Summary Statistics for Vital Signs	MS

[1] Added for final analysis

[2] Note that this table should be omitted for the final analysis and subsequent numbering updated as appropriate so there is no gap.

Commentato [MS2]: Removed as it is not in TOC

Commentato [MS3]: See comment above

16.3.2 Figures

Number	Title	Analysis Set
14.3.1.1.2	Individual Profiles of ANC from Screening to 100 Days Post-Treatment	MS
14.3.1.1.3	Individual Profiles of ANC from Screening to Last Post-Treatment Follow-Up	MS
14.3.2.3.2	Boxplots of Chemistry and Haematology Data, Relative to the Upper Limit of Normal, by Visit	MS
14.3.2.3.3	Boxplot of Haematology Data, Relative to the Lower Limit of Normal, by Visit	MS
14.3.2.3.4	Boxplot of Liver Function Test Data, Relative to the Upper Limit of Normal, by Visit	MS

14.3.2.3.5	Individual Profiles of LFT Relative to the Upper Limit of Normal Over Time	MS
14.3.2.4.2	Individual Profiles of Physical Growth (Height and Weight) Over Time	MS

16.3.3 Listings

Number	Title	Analysis Set
16.2.7.1	Listing of All Adverse Events	MS
16.2.7.2	Listing of Fatal Adverse Events	MS
16.2.7.3	Listing of All Serious Adverse Events	MS
16.2.7.4	Listing of Adverse Events Leading to Withdrawal from Study	MS
16.2.7.5	Listing of All Adverse Events Onset within 48 Hours from Infusion	MS
16.2.7.6	Listing of Predefined Adverse Event Groupings	MS
16.2.7.7	Listing of Relationship Between System Organ Class, Preferred Term, and Verbatim Text	MS
16.2.7.8	Listing of Adverse Events NCI CTCAE \geq 2 and Laboratory Features NCI CTCAE \geq 3 During the First 100 Days after Gene Therapy	MS
16.2.7.9	Listing of Hospitalisations	MS
16.2.8.1	Listing of Laboratory Data Outside Normal Range	MS
16.2.8.2	Listing of Laboratory Data	MS
16.2.8.3	Listing of Laboratory Tests and Associated Reference Ranges	MS
16.2.8.4	Listing of Vital Signs Data	MS
16.2.8.5	Listing of Absolute Neutrophil Count Response	MS

17 Appendix 2: Groupings for Medications, and Adverse Events related to Bleeds, Infections, Autoimmunity, Eczema or Suspected Malignancies

Grouping category	Terms
Medications	
Anti-infectives for systemic use	WHO-DD ATC 1 code J
Antineoplastic and immunomodulating agents	WHO-DD ATC 1 code L
Antimicrobials	WHO-DD coded term of: ACICLOVIR ACYCLOVIR AMOXICILLIN TRIHYDRATE;CLAVULANATE POTASSIUM AMOXICILLIN;CLAVULANATE POTASSIUM AMOXICILLIN;CLAVULANIC ACID AMPHOTERICIN B ANTIBIOTICS ANTIFUNGALS AZITHROMYCIN CEFAZOLIN CEFIXIME CEFTRIAXONE CEFTRIAXONE SODIUM CIPROFLOXACIN CIPROFLOXACIN HYDROCHLORIDE DAPSONE FLUCONAZOLE ITRACONAZOLE LEVOFLOXACIN MICAFUNGIN MICAFUNGIN SODIUM NYSTATIN PENTAMIDINE PENTAMIDINE ISETHIONATE SULFAMETHOXAZOLE;TRIMETHOPRIM VALGANCICLOVIR VALGANCICLOVIR HYDROCHLORIDE VORICONAZOLE
Blood and blood forming organs	WHO-DD ATC 1 code B
Dermatologicals	WHO-DD ATC 1 code D

Vaccines	WHO-DD ATC 2 J07
Infusion of platelets	WHO-DD coded term of PLATELETS, HUMAN BLOOD
Conditioning	WHO-DD coded terms of : RITUXIMAB BUSULFAN FLUDARABINE ANTITHYMOCYTE IMMUNOGLOBULIN
PBSC mobilization	Defined on PBSC eCRF page
IVIG infusion	WHO-DD ATC3 J06B is immunoglobulins.
Adverse Events	
Infections	MedDRA System Organ Class "INFECTIONS AND INFESTATIONS" Higher Level Group "MICROBIOLOGY AND SEROLOGY INVESTIGATIONS" in "INVESTIGATIONS" SOC Lower Level Terms 10003525 and 10022617 from SOC "RESPIRATORY, THORACIC AND MEDIASTINAL DISORDERS"

Bleeding	MedDRA Hemorrhage (excl Laboratory Terms) SMQ (Narrow) Abdominal wall haematoma Abdominal wall haemorrhage Abnormal withdrawal bleeding Achenbach syndrome Acute haemorrhagic leukoencephalitis Acute haemorrhagic ulcerative colitis Administration site bruise Administration site haematoma Administration site haemorrhage Adrenal haematoma Adrenal haemorrhage Anal fissure haemorrhage Anal haemorrhage Anal ulcer haemorrhage Anastomotic haemorrhage Anastomotic ulcer haemorrhage Aneurysm ruptured Angina bullosa haemorrhagica Anorectal varices haemorrhage Aortic aneurysm rupture Aortic dissection rupture Aortic intramural haematoma Aortic perforation Aortic rupture Aponeurosis contusion Application site bruise Application site haematoma Application site haemorrhage Application site purpura Arterial haemorrhage Arterial intramural haematoma Arterial perforation Arterial rupture Arteriovenous fistula site haematoma Arteriovenous fistula site haemorrhage Arteriovenous graft site haematoma Arteriovenous graft site haemorrhage Astringent therapy
----------	---

	Atrial rupture Auricular haematoma Basal ganglia haematoma Basal ganglia haemorrhage Basilar artery perforation Bladder tamponade Bleeding varicose vein Blood blister Blood urine Blood urine present Bloody discharge Bloody peritoneal effluent Bone contusion Bone marrow haemorrhage Brain contusion Brain stem haematoma Brain stem haemorrhage Brain stem microhaemorrhage Breast haematoma Breast haemorrhage Broad ligament haematoma Bronchial haemorrhage Bronchial varices haemorrhage Bursal haematoma Cardiac contusion Carotid aneurysm rupture Carotid artery perforation Catheter site bruise Catheter site haematoma Catheter site haemorrhage Central nervous system haemorrhage Cephalhaematoma Cerebellar haematoma Cerebellar haemorrhage Cerebellar microhaemorrhage Cerebral aneurysm perforation Cerebral aneurysm ruptured syphilitic Cerebral arteriovenous malformation haemorrhagic Cerebral artery perforation Cerebral haematoma Cerebral haemorrhage
--	--

	Cerebral haemorrhage foetal Cerebral haemorrhage neonatal Cerebral microhaemorrhage Cervix haematoma uterine Cervix haemorrhage uterine Chest wall haematoma Choroidal haematoma Choroidal haemorrhage Chronic gastrointestinal bleeding Chronic pigmented purpura Ciliary body haemorrhage Coital bleeding Colonic haematoma Conjunctival haemorrhage Contusion Corneal bleeding Cullen's sign Cystitis haemorrhagic Deep dissecting haematoma Diarrhoea haemorrhagic Disseminated intravascular coagulation Diverticulitis intestinal haemorrhagic Diverticulum intestinal haemorrhagic Duodenal ulcer haemorrhage Duodenitis haemorrhagic Dysfunctional uterine bleeding Ear haemorrhage Ecchymosis Encephalitis haemorrhagic Enterocolitis haemorrhagic Epidural haemorrhage Epistaxis Exsanguination Extra-axial haemorrhage Extradural haematoma Extravasation blood Eye contusion Eye haematoma Eye haemorrhage Eyelid bleeding Eyelid contusion
--	---

	Eyelid haematoma Femoral artery perforation Femoral vein perforation Foetal-maternal haemorrhage Fothergill sign positive Gastric haemorrhage Gastric ulcer haemorrhage Gastric ulcer haemorrhage, obstructive Gastric varices haemorrhage Gastritis alcoholic haemorrhagic Gastritis haemorrhagic Gastroduodenal haemorrhage Gastrointestinal haemorrhage Gastrointestinal polyp haemorrhage Gastrointestinal ulcer haemorrhage Gastrointestinal vascular malformation haemorrhagic Genital contusion Genital haemorrhage Gingival bleeding Graft haemorrhage Grey Turner's sign Haemarthrosis Haematemesis Haematochezia Haematocoele Haematoma Haematoma evacuation Haematoma infection Haematosalpinx Haematospermia Haematotympanum Haematuria Haematuria traumatic Haemobilia Haemophilic arthropathy Haemophilic pseudotumour Haemoptysis Haemorrhage Haemorrhage coronary artery Haemorrhage foetal Haemorrhage in pregnancy
--	--

	Haemorrhage intracranial Haemorrhage neonatal Haemorrhage subcutaneous Haemorrhage subepidermal Haemorrhage urinary tract Haemorrhagic adrenal infarction Haemorrhagic anaemia Haemorrhagic arteriovenous malformation Haemorrhagic ascites Haemorrhagic breast cyst Haemorrhagic cerebral infarction Haemorrhagic cyst Haemorrhagic diathesis Haemorrhagic disease of newborn Haemorrhagic disorder Haemorrhagic erosive gastritis Haemorrhagic hepatic cyst Haemorrhagic infarction Haemorrhagic necrotic pancreatitis Haemorrhagic ovarian cyst Haemorrhagic stroke Haemorrhagic thyroid cyst Haemorrhagic transformation stroke Haemorrhagic tumour necrosis Haemorrhagic urticaria Haemorrhagic vasculitis Haemorrhoidal haemorrhage Haemostasis Haemothorax Henoch-Schonlein purpura Hepatic haemangioma rupture Hepatic haematoma Hepatic haemorrhage Hereditary haemorrhagic telangiectasia Hyperfibrinolysis Hyphaema Iliac artery perforation Iliac artery rupture Iliac vein perforation Immune thrombocytopenic purpura Implant site bruising
--	---

	Implant site haematoma Implant site haemorrhage Incision site haematoma Incision site haemorrhage Increased tendency to bruise Induced abortion haemorrhage Inferior vena cava perforation Infusion site bruising Infusion site haematoma Infusion site haemorrhage Injection site bruising Injection site haematoma Injection site haemorrhage Instillation site bruise Instillation site haematoma Instillation site haemorrhage Internal haemorrhage Intestinal haematoma Intestinal haemorrhage Intestinal varices haemorrhage Intra-abdominal haematoma Intra-abdominal haemorrhage Intracerebral haematoma evacuation Intracranial haematoma Intracranial tumour haemorrhage Intraocular haematoma Intrapartum haemorrhage Intraventricular haemorrhage Intraventricular haemorrhage neonatal Iris haemorrhage Joint microhaemorrhage Kidney contusion Lacrimal haemorrhage Large intestinal haemorrhage Large intestinal ulcer haemorrhage Laryngeal haematoma Laryngeal haemorrhage Lip haematoma Lip haemorrhage Liver contusion Lower gastrointestinal haemorrhage
--	--

	Lower limb artery perforation Lymph node haemorrhage Mallory-Weiss syndrome Mediastinal haematoma Mediastinal haemorrhage Medical device site bruise Medical device site haematoma Medical device site haemorrhage Melaena Melaena neonatal Meningorrhagia Menometrorrhagia Menorrhagia Mesenteric haematoma Mesenteric haemorrhage Metrorrhagia Mouth haemorrhage Mucocutaneous haemorrhage Mucosal haemorrhage Muscle contusion Muscle haemorrhage Myocardial haemorrhage Myocardial rupture Naevus haemorrhage Nail bed bleeding Nasal septum haematoma Neonatal gastrointestinal haemorrhage Nephritis haemorrhagic Nipple exudate bloody Ocular retrobulbar haemorrhage Oesophageal haemorrhage Oesophageal intramural haematoma Oesophageal ulcer haemorrhage Oesophageal varices haemorrhage Oesophagitis haemorrhagic Optic disc haemorrhage Optic nerve sheath haemorrhage Oral contusion Oral mucosa haematoma Osteorrhagia Ovarian haematoma
--	---

	Ovarian haemorrhage Palpable purpura Pancreatic haemorrhage Pancreatitis haemorrhagic Papillary muscle haemorrhage Paranasal sinus haematoma Paranasal sinus haemorrhage Parathyroid haemorrhage Parotid gland haemorrhage Pelvic haematoma Pelvic haematoma obstetric Pelvic haemorrhage Penile contusion Penile haematoma Penile haemorrhage Peptic ulcer haemorrhage Pericardial haemorrhage Perineal haematoma Periorbital haematoma Periorbital haemorrhage Periosteal haematoma Peripartum haemorrhage Peripheral artery aneurysm rupture Peripheral artery haematoma Perirenal haematoma Peritoneal haematoma Peritoneal haemorrhage Periventricular haemorrhage neonatal Petechiae Pharyngeal haematoma Pharyngeal haemorrhage Pituitary haemorrhage Placenta praevia haemorrhage Polymenorrhagia Post abortion haemorrhage Post procedural contusion Post procedural haematoma Post procedural haematuria Post procedural haemorrhage Post transfusion purpura Postmenopausal haemorrhage
--	--

	Postpartum haemorrhage Post-traumatic punctate intraepidermal haemorrhage Premature separation of placenta Procedural haemorrhage Proctitis haemorrhagic Prostatic haemorrhage Pulmonary alveolar haemorrhage Pulmonary contusion Pulmonary haematoma Pulmonary haemorrhage Puncture site haemorrhage Purpura Purpura fulminans Purpura neonatal Purpura non-thrombocytopenic Purpura senile Putamen haemorrhage Radiation associated haemorrhage Rectal haemorrhage Rectal ulcer haemorrhage Renal artery perforation Renal cyst haemorrhage Renal haematoma Renal haemorrhage Respiratory tract haemorrhage Respiratory tract haemorrhage neonatal Retinal aneurysm rupture Retinal haemorrhage Retinopathy haemorrhagic Retroperitoneal haematoma Retroperitoneal haemorrhage Retroplacental haematoma Ruptured cerebral aneurysm Scleral haemorrhage Scrotal haematocoele Scrotal haematoma Shock haemorrhagic Skin haemorrhage Skin neoplasm bleeding Skin ulcer haemorrhage Small intestinal haemorrhage
--	--

	Small intestinal ulcer haemorrhage Soft tissue haemorrhage Spermatic cord haemorrhage Spinal cord haematoma Spinal cord haemorrhage Spinal epidural haematoma Spinal epidural haemorrhage Spinal subarachnoid haemorrhage Spinal subdural haematoma Spinal subdural haemorrhage Spleen contusion Splenic artery perforation Splenic haematoma Splenic haemorrhage Splenic varices haemorrhage Splinter haemorrhages Spontaneous haematoma Spontaneous haemorrhage Stoma site haemorrhage Stomatitis haemorrhagic Subarachnoid haematoma Subarachnoid haemorrhage Subarachnoid haemorrhage neonatal Subchorionic haematoma Subchorionic haemorrhage Subclavian artery perforation Subclavian vein perforation Subcutaneous haematoma Subdural haematoma Subdural haematoma evacuation Subdural haemorrhage Subdural haemorrhage neonatal Subgaleal haematoma Subgaleal haemorrhage Subretinal haematoma Superior vena cava perforation Testicular haemorrhage Thalamus haemorrhage Third stage postpartum haemorrhage Thoracic haemorrhage Thrombocytopenic purpura
--	--

	Thrombotic thrombocytopenic purpura Thyroid haemorrhage Tongue haematoma Tongue haemorrhage Tonsillar haemorrhage Tooth pulp haemorrhage Tooth socket haemorrhage Tracheal haemorrhage Traumatic haematoma Traumatic haemorrhage Traumatic haemothorax Traumatic intracranial haematoma Traumatic intracranial haemorrhage Tumour haemorrhage Ulcer haemorrhage Umbilical cord haemorrhage Umbilical haematoma Umbilical haemorrhage Upper gastrointestinal haemorrhage Ureteric haemorrhage Urethral haemorrhage Urinary bladder haemorrhage Urogenital haemorrhage Uterine haematoma Uterine haemorrhage Vaccination site bruising Vaccination site haematoma Vaccination site haemorrhage Vaginal haematoma Vaginal haemorrhage Varicose vein ruptured Vascular access site bruising Vascular access site haematoma Vascular access site haemorrhage Vascular access site rupture Vascular graft haemorrhage Vascular pseudoaneurysm ruptured Vascular purpura Vascular rupture Vein rupture Venous haemorrhage
--	--

	Venous perforation Ventricle rupture Vertebral artery perforation Vessel puncture site bruise Vessel puncture site haematoma Vessel puncture site haemorrhage Vitreous haematoma Vitreous haemorrhage Vulval haematoma Vulval haematoma evacuation Vulval haemorrhage Withdrawal bleed Wound haematoma Wound haemorrhage
--	---

Eczema/ dermatological	MedDRA defined terms list Acute generalized exanthematous pustulosis Administration site dermatitis Administration site eczema Administration site hypersensitivity Administration site rash Administration site recall reaction Administration site urticaria Administration site vasculitis Allergic eosinophilia Allergic granulomatous angiitis Allergic oedema Allergic otitis externa Allergic transfusion reaction Allergy alert test positive Allergy test positive Allergy to immunoglobulin therapy Allergy to vaccine Anaphylactic reaction Anaphylactic shock Anaphylactic transfusion reaction Anaphylactoid reaction Anaphylactoid shock Anaphylaxis treatment Angioedema Antiallergic therapy Anti-neutrophil cytoplasmic antibody positive vasculitis Application site dermatitis Application site eczema Application site hypersensitivity Application site rash Application site recall reaction Application site urticaria Application site vasculitis Atopy Blepharitis allergic Blood immunoglobulin E abnormal Blood immunoglobulin E increased Bromoderma Catheter site dermatitis Catheter site eczema Catheter site hypersensitivity Catheter site rash
---------------------------	--

	Catheter site urticaria Catheter site vasculitis Circumoral oedema Contact stomatitis Contrast media allergy Contrast media reaction Cutaneous vasculitis Dennie-Morgan fold Dermatitis Dermatitis acneiform Dermatitis allergic Dermatitis atopic Dermatitis bullous Dermatitis contact Dermatitis exfoliative Dermatitis exfoliative generalised Dermatitis herpetiformis Dermatitis infected Dermatitis psoriasiform Dialysis membrane reaction Documented hypersensitivity to administered product Drug cross-reactivity Drug eruption Drug hypersensitivity Drug provocation test Drug reaction with eosinophilia and systemic symptoms Eczema Eczema infantile Eczema nummular Eczema vaccinatum Eczema vesicular Eczema weeping Epidermal necrosis Epidermolysis Epidermolysis bullosa Erythema multiforme Erythema nodosum Exfoliative rash Eye allergy Eye oedema Eye swelling Eyelid oedema Face oedema
--	---

	Giant papillary conjunctivitis Gingival oedema Gingival swelling Gleich's syndrome Haemorrhagic urticaria Hand dermatitis Henoch-Schonlein purpura Henoch-Schonlein purpura nephritis Heparin-induced thrombocytopenia Hereditary angioedema Hypersensitivity Hypersensitivity vasculitis Idiopathic angioedema Idiopathic urticaria Immediate post-injection reaction Immune thrombocytopenic purpura Immune tolerance induction Implant site dermatitis Implant site hypersensitivity Implant site rash Implant site urticaria Incision site dermatitis Incision site rash Infusion site dermatitis Infusion site eczema Infusion site hypersensitivity Infusion site rash Infusion site recall reaction Infusion site urticaria Infusion site vasculitis Injection site dermatitis Injection site eczema Injection site hypersensitivity Injection site rash Injection site recall reaction Injection site urticaria Injection site vasculitis Instillation site hypersensitivity Instillation site rash Instillation site urticaria Interstitial granulomatous dermatitis Intestinal angioedema Iodine allergy
--	--

	Kaposi's varicelliform eruption Limbal swelling Lip oedema Lip swelling Mast cell degranulation present Medical device site dermatitis Medical device site eczema Medical device site hypersensitivity Medical device site rash Medical device site recall reaction Medical device site urticaria Mouth swelling Mucocutaneous rash Multiple allergies Nephritis allergic Nikolsky's sign Nodular rash Oculomucocutaneous syndrome Oculorespiratory syndrome Oedema mouth Oral allergy syndrome Oropharyngeal blistering Oropharyngeal spasm Oropharyngeal swelling Palatal oedema Palatal swelling Palisaded neutrophilic granulomatous dermatitis Palpable purpura Pathergy reaction Periorbital oedema Pruritus allergic Radioallergosorbent test positive Rash Rash erythematous Rash follicular Rash generalised Rash macular Rash maculo-papular Rash maculovesicular Rash morbilliform Rash neonatal Rash papulosquamous Rash pruritic
--	---

	Rash pustular Rash rubelliform Rash scarlatiniform Rash vesicular Reaction to azo-dyes Reaction to colouring Reaction to drug excipients Reaction to preservatives Red man syndrome Scrotal oedema Serum sickness Serum sickness-like reaction Skin necrosis Skin reaction Skin test positive Solar urticaria Solvent sensitivity Stevens-Johnson syndrome Stoma site hypersensitivity Stoma site rash Swelling face Swollen tongue Toxic epidermal necrolysis Toxic skin eruption Type I hypersensitivity Type II hypersensitivity Type III immune complex mediated reaction Type IV hypersensitivity reaction Urticaria Urticaria cholinergic Urticaria chronic Urticaria contact Urticaria papular Urticaria physical Urticaria pigmentosa Urticaria vesiculosa Vaccination site dermatitis Vaccination site eczema Vaccination site exfoliation Vaccination site hypersensitivity Vaccination site rash Vaccination site recall reaction Vaccination site urticaria
--	---

	Vaccination site vasculitis Vaccination site vesicles Vaginal exfoliation Vaginal ulceration Vasculitic rash Vessel puncture site rash Vulval ulceration Vulvovaginal rash Vulvovaginal ulceration
Autoimmunity	Investigator decision on eCRF page

18 Appendix 3: Schedule of Events

Pre and post-treatment evaluation (up to 36 months after gene therapy)

Parameter	Time point																								
	Clinical Exam.***	Routine lab. N° 1	Routine lab. N° 2	Bone Marrow+ qPCR			Microbiology N° 1	Microbiology N° 2	Microbiology N° 3	Immunology N° 1	Immunology N° 2	Immunology N° 3	Immunology N° 4	Immunology N° 5	Zhu score	HLA typing and donor search	WASP Expression**	Autoimmunity	PCR Transduced cells (PB)	Archiving Blood/BM sample	Specialist Examination	Imaging N° 1	Imaging N° 2	AEs/SAEs recording	Platelet activation and morphology
Screening	X	X		X*																					
Baseline	X	X	X		X	X				X	X	X	X	X		X	X		X	X	X	X			
Day -14	X	X					X																		
Day 0	X	X					X												X			X			
+ 7 days	X	X			X														X			X			
+ 14 days	X	X			X		X											X	X			X			
+ 21 days	X	X			X													X				X			
+ 30 days	X	X		X	X	X		X								X	X	X				X			
+ 60 days	X	X			X			X								X	X	X				X			
+ 90 days	X	X	X	X	X	X		X	X							X	X	X				X			
+ 180 days	X	X	X		X			X	X	X						X	X	X	X			X			
+ 1 y	X	X	X	X	X	X	X	X	X	X	X	X	X	X		X	X	X	X	X	X	X			
+ 1,5 y	X	X	X					X								X	X	X				X			
+ 2 y	X	X	X	X	X	X	X	X	X	X	X	X	X	X		X	X	X	X	X	X	X			
+ 2,5 y	X	X	X					X								X	X	X				X			
+ 3 y	X	X	X	X	X	X	X	X	X	X	X	X	X	X		X	X	X	X	X	X	X ^p			

* if the qPCR is not performed at this time point it may be performed on bone marrow collected for back up or harvested for preparation of medical product.

** WAS mutation search carried out at screening if not available

*** Eczema will be evaluated as part of the clinical examination (according to Imai, 2004)

^p Platelet activation and morphology will be assessed at at least one time point ≥ 3 years post-GT

Long-term follow up evaluation

Parameter	Clinical Exam.***	Routine Lab. N° 1	Routine Lab. N° 2	Bone Marrow+ qPCR	Microbiology N° 1	Microbiology N° 2	Microbiology N° 3	Immunology N° 2	Immunology N° 3	Immunology N° 4	Immunology N° 5	Zhu score	WASP Expression	Autoimmunity	PCR Transduced cells (PB)	Archiving Blood/BM sample	Specialist Examination	Imaging N° 3	Imaging N° 4	AEs/SAEs recording	Platelet activation and morphology
Time point																					
+ 4 y	X	X	X		X		X	X	X	X	X	X	X	X	X	X	X	X	X	X ^p	
+ 5 y	X	X	X	X	X	X	X	X	X	X	X	X	X	X	X	X	X	X	X	X ^p	
+ 6 y	X	X	X		X		X	X	X	X	X	X	X	X	X	X	X	X	X	X ^p	
+ 7 y	X	X	X		X		X	X	X	X	X	X	X	X	X	X	X	X	X	X ^p	
+ 8 y	X	X	X	X	X	X	X	X	X	X	X	X	X	X	X	X	X	X	X	X ^p	

*** Eczema will be evaluated as part of the clinical examination (according to Imai, 2004)

^p Platelet activation and morphology will be assessed at at least one time point ≥ 3 y post GT

Extended Long-Term Follow Up evaluation

Parameter	Year 9+ p.a. (+/- 3 months)
Social Life Is the patient living in a protected environment? Is the patient attending kindergarten/school or in employment (according to age)? - Please comment. How is the patient's social ability with peers (if applicable for age)? - If abnormal please specify. Does the patient practice any sport (if applicable for age)? - Please comment.	X
General Number of platelet infusions per year Complete Blood Count (CBC) including Platelet count/MPV	X
Specialist laboratory assessments Integration Site Analysis (ISA)	X
Safety* SAEs AEs (related to bleeds, infections, autoimmunity, eczema, suspected malignancies)	X
Ig usage** Intravenous Ig Subcutaneous Ig	X

* SAE and AE's related to bleeds, infections, autoimmunity, eczema or suspected malignancies will be forwarded to TIGET as per current practice by the physician overseeing the patient in their home country. This includes the event, labs, and any other relevant data. In addition patients/family may also provide such information directly to TIGET. All such AEs should be entered into the eCRF within 30 days of awareness. SAEs, and any suspected malignancies, should be reported within 24 hours of awareness.

** Frequency to be specified if possible.

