8.2.4. Expected AE/AR

The following reactions are expected following G-CSF + Plerixafor administration, conditioning regimen, other concomitant drug administration, and blood products and will be recorded if ≥ 2 CTCAE grade for clinical manifestations, ≥ 3 CTCAE grade for laboratory parameters:

- Vomiting
- Nausea
- Stomatitis
- Mucositis
- Diarrhea
- Hair loss
- Fever of undetermined origin during neutropenia
- Fatigue
- Loss of appetite
- Cytopenia
- Bleeding
- Headache
- Hypotension
- Hypertension
- Vasomotor effects, including flushing
- Dizziness
- Arthralgias
- Injection site reactions
- Allergic reactions (to transfusions or drugs different from the medicinal product)
- Electrolytes disturbances*
- Liver and renal function alterations*

**Abnormal laboratory values or test results constitute adverse events only if they induce clinical signs or symptoms or require therapy.*

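### The 'Eczema/dermatological' event grouping in SAP Appendix 2 is in effect a general hypersensitivity list, so a grouping-level count would include patients with no eczema or skin event

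*SAP*

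**What the plan says.** SAP 10.2.2.3 says that term lists will identify each type of event, and its heading names eczema as one type. It points to Appendix 2 (SAP section 17) for the terms in force when the SAP was written. Appendix 2 has one row bearing on eczema, labelled eczema/dermatological and defined by a MedDRA term list. Besides eczema, dermatitis, rash and urticaria terms, that row contains:

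- "Anaphylactic reaction Anaphylactic shock Anaphylactic transfusion reaction Anaphylactoid reaction Anaphylactoid shock"
- "Allergic transfusion reaction Allergy alert test positive Allergy test positive Allergy to immunoglobulin therapy Allergy to vaccine Anaphylactic reaction Anaphylactic shock"
- "Blood immunoglobulin E abnormal Blood immunoglobulin E increased"
- "Immediate post-injection reaction Immune thrombocytopenic purpura Immune tolerance induction"
- heparin-induced thrombocytopenia, allergic nephritis, serum sickness, contrast media and dialysis membrane reactions, and type I to IV hypersensitivity terms.

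The output whose title matches the row is safety Table 14.3.2.2.13, "Number (%) of Subjects with Eczema and Dermatological Adverse Events by Preferred Term and Treatment Phase", on the mobilisation set. Listing 16.2.7.6 lists the predefined event groupings.

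The secondary efficacy endpoint is defined elsewhere. SAP 9.2.6 and Protocol 4.3.2(e) use a four-level investigator score from the clinical examination. It is reported in Table 14.2.2.4.1, Figure 14.2.2.4.2 and Listing 16.2.6.12.

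From year 9, the extended follow-up schedule (Protocol Table 8c; SAP Appendix 3) has no clinical examination and no eczema score. Its safety row collects SAEs and "AEs (related to bleeds, infections, autoimmunity, eczema, suspected malignancies".

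**The concern.** A grouping with eczema first in its name will be read as telling the reader how many patients had eczema or another skin event in each phase. As defined, a patient whose only listed event was a transfusion reaction, an anaphylactic reaction or an immune thrombocytopenia is counted too.

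Such events are foreseeable here. Protocol 8.2.4 lists "Allergic reactions (to transfusions or drugs different from the medicinal product" among the expected reactions. Patients may receive platelets, immunoglobulin, rituximab, ATG and vaccines. SAP 10.2.2.1 builds the adverse event tables from the medical history and concomitant disease pages as well as the adverse event page, so reactions during conditioning enter the on-treatment phase. The non-skin events would therefore tend to fall around conditioning and in early follow-up, which is where a by-phase table would show them.

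Four terms also sit in the Bleeding list, and no rule says how a shared term is assigned. At stake is the meaning of a supportive safety grouping, chiefly in the years when no eczema score is taken.

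**Working it through.** The plan states no figure for this grouping, so there is nothing to reproduce. The check is a count of the list and an overlap check. The printed list runs on without separators, so it was split by hand and the counts are approximate.

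**1. Composition of the row (SAP Appendix 2)**

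| Terms | Count | Share of 223 |
|---|---|---|
| All terms | 223 | 100% |
| Containing eczema, dermatitis, rash or urticaria | 88 | 88/223 = 39% |
| Containing eczema or dermatitis | 36 | 36/223 = 16% |
| Containing eczema | 13 | 13/223 = 6% |
| Of those, administration- or device-site terms | 7 | |
| Of those, not site terms | 13 − 7 = 6 | 6/223 = 2.7% |

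The six non-site terms are eczema itself and the infantile, nummular, vaccinatum, vesicular and weeping forms. Dermatitis atopic is a seventh natural candidate.

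**2. Terms that fit neither half of the label**

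A keyword search for anaphylaxis, transfusion, immunoglobulin E, thrombocytopenia, positive tests, contrast media, angioedema, nephritis, therapy and vaccine finds 26 terms (26/223 = 12%). Nearly all are systemic, laboratory or non-skin. The search misses others of the same kind, such as drug hypersensitivity, serum sickness and dialysis membrane reaction. The 26 therefore shows scale and is not a classification.

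**3. Overlap with the Bleeding list**

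Four terms are in both rows: immune thrombocytopenic purpura, Henoch-Schonlein purpura, palpable purpura and haemorrhagic urticaria.

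**4. Effect on a percentage of subjects**

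One patient counted only for a non-skin term adds 100/N percentage points, where N is the size of the mobilisation set. The SAP plans 8 treated patients. The mobilisation set is everyone who started mobilisation or harvest (SAP 7.1), so N may exceed 8.

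- N = 8: 100/8 = 12.5 points
- N = 9: 100/9 = 11.1 points
- N = 10: 100/10 = 10.0 points

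Two such patients with N = 8 would turn 0% into 2/8 = 25%.

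**5. Where the list reaches and where it does not**

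- Eczema efficacy outputs through year 8: based on the score; Appendix 2 is not used.
- Table 14.3.2.2.13 and Listing 16.2.7.6: titled for this grouping and the predefined groupings, so they depend on Appendix 2.
- General outputs by preferred term (Table 14.3.2.2.2, Listing 16.2.7.1): independent of Appendix 2.
- Year 9 onward: no score, so scheduled eczema evidence is adverse-event based. Appendix 2 is the SAP's only rule for grouping it.

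**The case against.** The strongest reply is that this is a supportive safety table whose title says eczema and dermatological. Rash, urticaria and dermatitis belong under that title, so testing the list against eczema alone (2.7%) judges it on a scope it does not claim. That is right. The defect is confined to terms that are neither eczema nor skin.

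Second, the table is by preferred term, so an anaphylactic reaction prints under its own name and eczema has its own row. The shells are in a separate document (SAP section 8), and no total row is shown in the SAP. This also stands. The distortion falls on a grouping-level count, if one is produced, and on the grouping in Listing 16.2.7.6.

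Third, SAP 10.2.2.1 plans a manual search alongside the listing of these events, and 10.2.2.3 lets the term list be revised at reporting. This makes correction easy. However, the stated grounds for revision are dictionary changes and emerging data, with no commitment to remove ill-fitting terms.

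Fourth, raised IgE has a disease link: Protocol 1.1.3.3 associates it with eczema in this syndrome. The note to Protocol 8.2.4 treats laboratory abnormalities as adverse events only if they cause symptoms or need therapy. Raised IgE alone may therefore rarely be counted.

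Some stronger readings are tempting, and the documents do not support them:

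- A reader might infer that the secondary eczema endpoint is biased. It uses the score and never draws on Appendix 2.
- A reader might infer that the table would show eczema worsening after it had cleared. That needs a total row the SAP does not show, and a reader who ignores both the preferred-term rows and the score shift table.
- A reader might infer that after year 8 this grouping is the only eczema measure. Eczema events are collected as such and appear by preferred term in the general outputs. Non-serious events are collected then only in the five named categories, so a non-serious transfusion or drug reaction is outside what is scheduled.
- A reader might infer that shared terms are double-counted. The groupings feed separate outputs, and no planned output adds them together. The gap is a missing assignment rule.

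**Conclusion.** The point holds as a minor defect of definition. The row is in effect a general hypersensitivity list: about 223 terms, 13 containing eczema (7 of them site reactions), and a substantial minority that are systemic, laboratory or haematological. Any grouping-level subject count in Table 14.3.2.2.13, and the eczema group in Listing 16.2.7.6, would include patients with no eczema or skin event.

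The size is 12.5 percentage points per such patient if the mobilisation set is 8, and less if it is larger. The conclusion rests on the hand-split counts, on Table 14.3.2.2.13 using the Appendix 2 row that its title matches, and on a grouping-level count being reported.

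The efficacy conclusion on eczema is not in question through year 8. After year 8 the grouping carries more weight because no score is scheduled, although the general adverse event outputs still show eczema events by name.

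**What to change.** Split the Appendix 2 row in two:

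1. Eczema: a subset confirmed at medical review, for example the six non-site eczema terms and dermatitis atopic.
2. Hypersensitivity/other dermatological: the remaining terms.

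Show the two as separate blocks in Table 14.3.2.2.13 and Listing 16.2.7.6. State that any adverse-event-based statement about eczema rests on the first group only. Add a rule for assigning the four terms shared with the Bleeding list: immune thrombocytopenic purpura, Henoch-Schonlein purpura, palpable purpura and haemorrhagic urticaria.

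The cost is an edit to Appendix 2 and one more table block. No data are lost, and SAP 10.2.2.3 already allows the list to change before reporting. The downside is that an eczema flare coded only as rash moves to the second group, where it stays visible.
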